APPENDIX 4 CRITERIA TO ASSESS SEVERITY OF LIVER-RELATED ADVERSE EVENTS

Parameter	Grade 0	Grade 1	Grade 2	Grade 3	Grade 4
ALT	<1.25	1.25-2.5	>2.5-5.0	>5.0-10	>10
AST	<1.25	1.25-2.5	>2.5-5.0	>5.0-10	>10
Alkaline Phosphatase	<1.25	1.25-2.5	>2.5-5.0	>5.0-10	>10
GGT	<1.25	1.25-2.5	>2.5-5.0	>5.0-10	>10
Bilirubin	Normal	>1.0-1.5	>1.5-2.5	>2.5-5	>5

Abbreviations: ALT = alanine aminotransferase; AST = aspartate aminotransferase; GGT = gamma glutamyl transferase.

Note: Values expressed as multiples of the upper limit of the normal range (ULN).

APPENDIX 5 STOPPING RULES FOR LIVER-RELATED BLOOD TESTS

Treatment-Emergent ALT	Treatment-Emergent TBL	Symptoms	Action
Normal baseline ^a : ALT >5 × ULN	Normal	None	Repeat ALT, AST, ALP, TBL, in 2–5 days
Elevated baseline: ALT >3 × baseline or >300 U/L (whichever occurs first)	For patients with Gilbert's syndrome: No change in baseline TBL		Follow-up for symptoms.
Normal baseline: ALT >8 × ULN	Normal	None	Interrupt study drug.
Elevated baseline: ALT >8 × baseline or >500 U/L (whichever occurs first)	Patients with Gilbert's syndrome: No change in baseline TBL		Initiate close monitoring and workup for competing etiologies. Study drug can be restarted only if another etiology is identified and liver enzymes return to baseline.
Normal baseline: ALT >5 × ULN	TBL >2 × ULN	None	Interrupt study drug.
Elevated baseline: ALT >3 × baseline or >300 U/L (whichever occurs first)	For patients with Gilbert's syndrome: Doubling of direct bilirubin		Initiate close monitoring and workup for competing etiologies. Study drug can be restarted only if another etiology is identified and liver enzymes return to baseline.
Normal baseline: ALT >5 x ULN	Normal or elevated	i.e. Severe fatigue, nausea, vomiting, right upper quadrant pain	Interrupt study drug.
Elevated baseline: ALT >3 x baseline or >300 U/L (whichever occurs first)			Initiate close monitoring and workup for completing etiologies. Study drug can be restarted only if another etiology is identified and liver enzymes return to baseline.

ALP=alkaline phosphatase; ALT=alanine aminotransferase; AST=aspartate aminotransferase; TBL=total bilirubin; ULN=upper limit of normal.

^aBaseline is Visit 2

Source: [Chalasani and Regev, 2016](#).

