7.1.3 Treatment and Assessment Period (Visits 3 through 9/EOS)

During the 48 weeks of double-blind treatment, 7 clinic visits are scheduled to occur as follows:

- Visit 3 - Week 2, Day 14 (+/- 3 days)
- Visit 4 - Week 4, Day 28 (+/- 3 days)
- Visit 5 - Week 8, Day 56 (+/- 5 days)
- Visit 6 - Week 12, Day 84 (+/- 5 days)
- Visit 7 - Week 24, Day 168 (+/- 7 days) – Interim Analysis
- Visit 8 - Week 36, Day 252 (+/- 7 days)
- Visit 9 - Week 48, Day 336 (+/- 7 days) – End of Study

Subjects are reminded not to eat and not to take their study drug on the day of scheduled study visits prior to completion of assessments. They should bring their study drug with them to the visit. IP should be taken 30 minutes prior to the first meal of the day containing approximately 10-20 grams of fat.

The Schedule of Assessments provided in [Table 1](#) details the procedures to be completed at each visit. All Treatment visits (3 through 9) will include weight and waist/hip measurements, assessment of vital signs, and blood sampling for completion of biochemistry, hematology, serum glucose, lipid panel, HbA1c, and serum liver-related blood tests. At all visits, adverse events, and concomitant medications will be collected for all subjects, and female subjects of childbearing potential will have a urine pregnancy test. Subjects will return containers of unused study drug for assessment of accountability and compliance which will be documented in the IRT. New supplies of study drug will be dispensed at Visits 3 through 8.

Additional assessments will also occur less frequently during the Treatment Period for vitamin A, vitamin D, vitamin E, vitamin K via PT/INR, insulin, thyroid testing, urinalysis, ECG, physical examinations, stool assessment, and completion of the EQ-5D-5L.

An MRI will be repeated at Visit 7 for the 24-week IA and at Visit 9 (Week 48) for all subjects. A final liver biopsy will be performed at Visit 9 (Week 48) for all subjects unless a subject discontinues prior to Week 44, in which case the EOS liver biopsy is not required.

Sites that have supplied local slides for central reading for subject eligibility at Screening must also provide local liver histology slides for the subject to be centrally read for the Week 48 EOS liver biopsy. The central reader will provide the final liver histology assessment for Week 48.

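### Appendix 5 lists no action for an asymptomatic subject without Gilbert's syndrome whose bilirubin rises to >1 to 2 × ULN, so a listed drug interruption lapses as the liver profile worsens

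*Protocol*

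**What the plan says.** Appendix 5 has four rows, numbered here from the top. Each combines an ALT threshold, a condition under the heading "Treatment-Emergent TBL", a symptom condition and an action.

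- Row 1: normal baseline, ALT >5 × ULN; elevated baseline, ALT >3 × baseline or >300 U/L. Bilirubin normal, no symptoms. Action: "Repeat ALT, AST, ALP, TBL, in 2–5 days", with follow-up for symptoms.
- Row 2: "Normal baseline: ALT >8 × ULN"; elevated baseline, >8 × baseline or >500 U/L. Bilirubin normal, no symptoms. Action: interrupt drug.
- Row 3: the row 1 ALT thresholds, bilirubin >2 × ULN, no symptoms. Action: interrupt drug.
- Row 4: the row 1 ALT thresholds, bilirubin either normal or elevated, symptoms present. Action: interrupt drug.

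Gilbert's syndrome has its own bilirubin conditions. Rows 1 and 2 use "patients with Gilbert's syndrome: No change in baseline TBL" (the capitalisation differs slightly between them), and row 3 uses "For patients with Gilbert's syndrome: Doubling of direct bilirubin".

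Sections 4.5.4 and 8.1.6 point to Appendix 5 and add no ALT or bilirubin threshold of their own.

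**The concern.** A stopping rule should not become weaker as the laboratory picture gets worse. This one does. With ALT already high enough to interrupt drug at normal bilirubin, a small rise in bilirubin takes the subject out of row 2 without bringing the subject into row 3. Read as written, the table then asks for nothing.

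A joint rise in ALT and bilirubin is the pattern such a table exists to catch, and the rule has to be applied in the same way at 60 to 80 sites. If a site follows it literally, dosing continues and no early retest is required. Section 6.2 supplies each subject with enough drug to last until the following visit.

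**Working it through.** **1. Does the word Normal in rows 1 and 2 reach up to 2 × ULN?** No. Row 4 accepts bilirubin that is normal or elevated, so the table itself separates the two. Appendix 4 states its limits as "Values expressed as multiples of the upper limit of the normal range (ULN") and puts bilirubin of >1.0–1.5 in Grade 1, one step above normal. Grade 2 is >1.5–2.5.

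**2. Apply the rows to an asymptomatic subject without Gilbert's syndrome.**

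| ALT | Bilirubin normal | >1 to 2 × ULN | >2 × ULN |
|---|---|---|---|
| Normal baseline, >5 to 8 × ULN | Row 1: repeat in 2–5 days | No row | Row 3: interrupt |
| Normal baseline, >8 × ULN | Row 2: interrupt | No row | Row 3: interrupt |
| Elevated baseline, above 3 × baseline or 300 U/L but below the row 2 limit | Row 1: repeat in 2–5 days | No row | Row 3: interrupt |
| Elevated baseline, >8 × baseline or >500 U/L | Row 2: interrupt | No row | Row 3: interrupt |

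Spot values confirm this. At ALT 9 × ULN with a normal baseline, bilirubin of 0.8 gives interruption; 1.01, 1.5 and 2.0 match no row; 2.01 and 3 give interruption. With symptoms, row 4 gives interruption at every one of these values.

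**3. Where the band lies on the protocol's own scale.** Bilirubin >1.0 to 2.0 × ULN is all of Grade 1 and the part of Grade 2 up to 2.0. For normal-baseline subjects it coincides with ALT Grade 3 (>5–10 × ULN) or Grade 4 (>10 × ULN).

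**4. What else in the protocol applies.**
- Section 4.5: the investigator or sponsor may withdraw a subject at any time.
- Section 4.5.1: medically important events may lead to withdrawal.
- Section 7.2.3.5: unexplained abnormal values may be repeated, at discretion.
- Section 8.1.5: the investigator decides whether a laboratory change is an adverse event.
- Section 8.1 and Table 1 footnote v: adverse events must be followed to closure.

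The last of these is mandatory once an event is recorded. None of them requires interruption or sets a retest interval.

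**5. Time to the next scheduled liver panel.** Section 7.1.3 places Visits 6 to 9 at Days 84, 168, 252 and 336, for example "Visit 7 - Week 24, Day 168 (+/- 7 days") and "Visit 8 - Week 36, Day 252 (+/- 7 days"). Visit 6 has a ±5 day window and Visit 9 a ±7 day window.

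- Nominal: 168 − 84 = 84; 252 − 168 = 84; 336 − 252 = 84 days.
- Longest with windows: Visit 6 to 7, (168 + 7) − (84 − 5) = 96; Visit 7 to 8, (252 + 7) − (168 − 7) = 98; Visit 8 to 9, (336 + 7) − (252 − 7) = 98 days.
- Found earlier, at Week 2, 4 or 8: 28 − 14 = 14; 56 − 28 = 28; 84 − 56 = 28 days.

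The comparison is with 2–5 days in row 1.

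**6. Is this an artefact of the text extraction?** The superseded Amendment 3 table in the same file has the same row structure, so that is unlikely.

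**The case against.** The strongest reply is clinical. Section 8.1.6 calls the appendix guidelines, and a physician told to stop drug at ALT >8 × ULN with normal bilirubin would hardly continue because bilirubin has risen too. The protocol also gives that physician the means to act. ALT above 5 × ULN is Grade 3 on the liver scale, Section 7.2.3.5 asks for significant findings to be assessed for recording as adverse events, and recorded events must be followed to closure. Section 4.5.4 adds continuous safety monitoring and Section 9.5.2 regular review by the monitoring committee. The table is also attributed to a published source that is not available here and may have accompanying text on the intermediate band.

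Most of this stands as mitigation, and it limits the consequence that can be claimed. It does not close the gap. The appendix is titled as stopping rules, and a site working from the protocol has only the protocol's rows.

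Four stronger readings are tempting, and the documents do not support them.

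- A reader might infer that subjects in the band would go untouched for 84 to 98 days, or that this risk runs through most of the treatment period because the three long intervals fill most of it. The long wait applies only to an abnormality first found at Week 12, 24 or 36, and only if nobody uses the discretion or follow-up available. After Weeks 2, 4 and 8 the next visit is 14 to 28 days away, and at Week 48 dosing is over.
- A reader might extend the gap to everyone with Gilbert's syndrome. Those with unchanged bilirubin are covered by rows 1 and 2. A parallel gap exists only if total bilirubin rises without direct bilirubin doubling.
- A reader might add subjects who enter at >1 to 2 × ULN, which exclusion criterion 15 allows, and stay there. The column heading refers to treatment-emergent bilirubin, so their position is ambiguous rather than clearly uncovered.
- A reader might treat the mention of AST in Section 8.1.6, for which Appendix 5 has no trigger, as part of this defect. It is a separate matter, and simply deleting AST would not be the protective choice.

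**Conclusion.** The gap is real and should be fixed. Above the table's ALT thresholds, an asymptomatic subject without Gilbert's syndrome whose bilirubin rises on treatment to >1 and up to 2 × ULN has no listed action. Above the row 2 ALT limit the subject loses a listed interruption; below it, only the 2–5 day repeat is lost.

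The finding about the table rests on Normal meaning no more than 1 × ULN, which row 4 and Appendix 4 both support. The practical consequence is less certain. The 84-day wait (up to 98) is a worst case and assumes that no one acts outside the table. The number of subjects affected cannot be derived from the protocol. The point concerns participant safety and bears on no efficacy estimate, error rate or sample size.

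**What to change.** Change two bilirubin cells in Appendix 5.

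- Row 2: remove the bilirubin condition, so that ALT >8 × ULN (elevated baseline: >8 × baseline or >500 U/L) interrupts drug at any bilirubin.
- Row 1: replace Normal with total bilirubin ≤2 × ULN and, for Gilbert's syndrome, direct bilirubin not doubled. This is the minimum; the sponsor's hepatology lead may prefer a stricter action for >1 to 2 × ULN.

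For a normal baseline without symptoms, the result is as follows. At ALT >5 to 8 × ULN, bilirubin ≤2 × ULN goes to row 1 and >2 × ULN to row 3. At ALT >8 × ULN, any bilirubin means interruption. Above the table's ALT thresholds every asymptomatic bilirubin level then has an action, and the action never weakens as bilirubin rises. Below those thresholds the table stays silent, as it is now.

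The edit fits in the next amendment. It changes no scheduled visit, scheduled sample or sample size; its running cost is the occasional unscheduled retest or interruption in the band now left out.

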Table 1 Schedule of Assessments	Revised footnote “k” to clarify that subjects are not required to have Vitamin A, D, and E testing at the screening visit.	
 • To eliminate additional blood tests.
Table 1 Schedule of Assessments	Revised footnote “r” to clarify that HCVRNA would be performed only if HCVAb is positive.	
 • To improve clarity.
Table 1 Schedule of Assessments	Added footnote “c” to indicate that Visit 9 MRI and liver biopsy procedures are required to be completed within +14 days of Visit 9.	
 • Ensures that Visit 9 liver biopsy and MRI are done after the last dose of study drug.
Table 1 Schedule of Assessments	Added footnote “d” to clarify that subjects who have failed screening may be re-screened.	
 • To allow the rescreening of subjects who previously screen failed, once their eligibility status has changed from the initial screening visit.
Section 3.1 Study Design and Flow Chart, Synopsis	Added mention that the number of F0 subjects will be capped at 81 if 1 dose is dropped after the interim analysis and at 62 if 2 doses are dropped.	
 • To allow for a limited number of subjects without fibrosis to be enrolled.
Section 3.1 Study Design and Flow Chart, Synopsis	Added mention that 208 subjects are needed for analysis if 1 or 2 doses of SHP626 are dropped after the interim analysis.	
 • To improve clarity.

Protocol Amendments		
Summary of Change(s) Since Last Version of Approved Protocol		
Amendment Number	Amendment Date	Global/Country/Site Specific
3	22 March 2017	Global
Section(s) Affected by Change	Description of Change	Rationale
Section 4.1 Inclusion Criteria, Synopsis	Criterion #6 was revised to allow for F0 (fibrosis score), in addition to F1-F3.	
 To allow for subjects without fibrosis to be eligible for enrollment.
Section 4.2 Exclusion Criteria, Synopsis	Revised criterion #5 to include: “Stents or other devices may be allowed, at the investigator’s discretion, if they do not interfere with the functioning of the MRI machine.”	
 To allow for inclusion of subjects having these devices, at the discretion of the investigator.
Section 4.2 Exclusion Criteria, Synopsis	Criterion #8 was revised to update the definition of uncontrolled diabetes (HbA1c \geq 9.5% within 60 days prior to enrollment).	
 To allow for patients with up to 9.5% HbA1c to be eligible for participation.
Section 4.2 Exclusion Criteria, Synopsis	Revised criterion #9 to clarify that insulin dose may be adjusted after screening/enrollment as long as the subject’s HbA1c remains <9.5%.	
 To allow for inclusion of subjects who may need to adjust insulin dose during the study.
Section 4.2 Exclusion Criteria, Synopsis	Revised criteria #11 and #12 to allow for enrollment of subjects with elevation in AST (#11) and ALT (#12) up to 7 times the ULN (instead of 5 times the ULN).	
 It was determined that elevations up to this point (\leq7 times ULN) in AST and ALT should not preclude subject participation and does not expose such subjects to any additional safety risks.
Section 4.2 Exclusion Criteria, Synopsis	Revised criterion #30 to remove exclusion of subjects who previously failed screening.	
 To allow the rescreening of subjects who previously screen failed, once their eligibility status has changed from the initial screening visit.
Section 4.2 Exclusion Criteria, Synopsis	Revised criterion #31 regarding exclusion of investigational study site employees.	
 To improve clarity.
Section 5.2.2 Prohibited Treatment	Added obeticholic acid to the list of prohibited treatments.	
 Prohibited this medication as there is potential for a drug to affect NASH.
Section 5.2.2 Prohibited Treatment	Clarified that tetracycline dose limit is \leq 1 g per day.	
 To improve clarity.
Section 5.2.2 Prohibited Treatment	Clarified that estrogen dose $>$ 2 mg QD is prohibited.	
 To improve clarity.

Protocol Amendments		
Summary of Change(s) Since Last Version of Approved Protocol		
Amendment Number	Amendment Date	Global/Country/Site Specific
3	22 March 2017	Global
Section(s) Affected by Change	Description of Change	Rationale
Section 5.2.2 Prohibited Treatment	Changed text from “drugs cannot have been taken for more than 2 weeks within the year prior to randomization” to: “drugs cannot have been taken for more than 2 weeks within the 6 months prior to randomization”	
 To enable a less strict requirement without affecting safety.
Section 6.2.2 Allocation of Subjects to Treatment	Added mention that the number of F0 subjects will be capped at 81 if 1 dose is dropped after the interim analysis and at 62 if 2 doses are dropped.	
 To allow for a limited number of subjects without fibrosis to be enrolled.
Section 6.2.3 Dosing	Added mention that if a dose is missed at the normally scheduled time, the subject can make up the dose that day as long as no more than 1 dose is taken in a 10-hour period.	
 To specify parameters regarding dosing time if a dose is missed
Section 7.1.1 Screening (Visit 1)	Revised passage to indicate subjects designated as screen failures could be re-screened once.	
 To allow the rescreening of subjects who previously screen failed when their eligibility status has changed from the initial screening visit.
Section 7.1.1 Screening (Visit 1)	Added description of process for providing additional liver tissue to the central reader.	
 To allow additional liver tissue to be sent to the central reader.
Section 7.1.2 Baseline (Visit 2)	Added mention that subjects are randomized using IRT before the IA and then to 1 of the remaining arms after the IA.	
 To improve clarity.
Section 7.1.3 Treatment and Assessment Period (Visits 3 through 9/EOS)	Added details of the liver histology assessment at Week 48.	
 To improve clarity.
Section 7.2.3.6 Additional Laboratory Assessments	Clarified that HCVRNA would be performed only if HCVAb is positive.	
 To improve clarity.
Section 7.2.3.6 Additional Laboratory Assessments	Revised to clarify that Vitamin A, D, and E testing are not required at screening.	
 To improve clarity. Alignment with Table 1.

Protocol Amendments		
Summary of Change(s) Since Last Version of Approved Protocol		
Amendment Number	Amendment Date	Global/Country/Site Specific
3	22 March 2017	Global
Section(s) Affected by Change	Description of Change	Rationale
Section 9.3 Data Handling and Considerations	Removed “IP serum concentrations, antibiotics to investigation product” from the parenthetical list of data items that could potentially unblind treatment assignment.	
 • To correct an error.
Section 9.6 Sample Size Calculation and Power Considerations, Synopsis	Increased approximate number of subjects screened from 334 to 677 subjects.	
 • To accommodate a higher screen failure rate.
Section 9.6 Sample Size Calculation and Power Considerations, Synopsis	Added specificity with regard to number of subjects needed for analysis if more than 1 dose/dosing arm is dropped following the interim analysis.	
 • To improve clarity.
Section 9.7 Study Population	Added definition of “The Randomized Set.”	
 • To improve clarity.
Section 9.8 Efficacy Analyses	Clarified that the efficacy analyses involving statistical testing will only be done for the doses that are not dropped at the interim analysis.	
 • To improve clarity.
Section 9.8.1 Primary Efficacy Endpoint	Clarified that the method for handling missing data in the primary analysis is non-responder imputation.	
 • To improve clarity.
Section 9.8.2 Secondary Efficacy Endpoints	The definition of “Resolution of NASH” was revised.	
 • To allow consistency with newly revised and recommended definition.
Throughout protocol.	Minor changes to format and correct typos.	
 • To improve clarity.

EMERGENCY CONTACT INFORMATION

In the event of a serious adverse event (SAE), the investigator must fax or e-mail the Shire Clinical Study Serious Adverse Event and Non-serious Adverse Events (AEs) Required by the Protocol Form within 24 hours to:

Shire Global Drug Safety Department

Preferred method: scan and e-mail to [contact]
OR fax to [contact] (Global); or [contact] (North America)

AND

A copy of this form must also be sent to the Shire GCDL by fax or e-mail using the details below:

[name], FAASLD, GCDL-Hepatology

[contact]

e-mail: [contact]

For protocol- or safety-related issues during normal business hours 9:00 a.m. to 5:00 p.m. (Eastern Time), the investigator must contact the Contract Research Organization (CRO) Medical Monitor:

ICON Medical Monitor: [name]

[contact]

[contact]

[contact]

ALT	alanine aminotransferase
aPPT	activated partial thromboplastin time
ASBT	apical sodium-dependent bile acid transporter
ASBTi	ASBT inhibitor
AST	aspartate aminotransferase
β-HCG	beta-human chorionic gonadotropin
BA	bile acid
BMI	body mass index
C4	7-alpha-hydroxy-4-cholesten-3-one
CRA	clinical research associate
CRC	clinical research center
CRO	contract research organization
DMC	data monitoring committee
eCRF	electronic case report form
EQ-5D-5L	EuroQol-5 Dimension-5 Level Questionnaire
ECG	electrocardiogram
EOS	end of study
EU	European Union
FAS	full analysis set
FBA	fecal bile acid
FDA	Food and Drug Administration
FXR	farnesoid X receptor
GCDL	Global Clinical Development Lead
GCP	Good Clinical Practice
GDS	Global Drug Safety
GGT	gamma glutamyl transferase
GLP-1 RA	glucagon-like peptide-1 receptor agonists
HbA1c	hemoglobin A1c
HBcAb	hepatitis B core antibody
HBsAg	hepatitis B surface antigen
HBV	hepatitis B virus

HBVDNA	hepatitis B virus deoxyribonucleic acid
HCV	hepatitis C virus
HCVAb	hepatitis C virus antibody
HCVRNA	hepatitis C virus ribonucleic acid
HDL-C	high-density lipoprotein-cholesterol
HFD	high fat diet
HFF	hepatic fat fraction
HIPAA	Health Insurance Portability and Accountability Act
HIV	human immunodeficiency virus
HOMA-%B	homeostasis model assessment in β -cell function
HOMA-IR	homeostasis model assessment insulin resistance
HRQoL	health-related quality of life
IA	interim analysis
IAS	interim analysis set
ICH	The International Council for Harmonisation of Technical Requirements for Pharmaceuticals for Human Use
IND	investigational new drug
INR	international normalized ratio
IP	investigational product
IR	insulin resistance
IRB	Institutional Review Board
IRT	interactive response technology
LDL-C	low-density lipoprotein-cholesterol
MCH	mean corpuscular hemoglobin
MCV	mean corpuscular volume
MedDRA	Medical Dictionary for Regulatory Activities
MR	magnetic resonance
MRI	magnetic resonance imaging
MRS	magnetic resonance spectroscopy
MOA	mechanism of action
NAFLD	nonalcoholic fatty liver disease
NAS	NAFLD Activity Score
NASH	nonalcoholic steatohepatitis
NASH CRN	NASH Clinical Research Network
NOAEL	no observed adverse effect level
PBC	primary biliary cirrhosis

PBO	placebo
PDFF	proton density fat-fraction
PO	by mouth
POC	proof of concept
PRO	patient-reported outcome
PSC	primary sclerosing cholangitis
PT	prothrombin time
QD	once daily
RBC	red blood cell
SAE	serious adverse event
SAF	steatosis, activity, and fibrosis score
SAP	statistical analysis plan
T2DM	type 2 diabetes mellitus
T3	triiodothyronine
TA	therapeutic area
TB	total bilirubin
TEAE	treatment-emergent adverse event
TGR5	transmembrane G protein-coupled receptor
TPN	total parenteral nutrition
TSH	thyroid-stimulating hormone
TZD	thiazolidinediones
ULN	upper limit of normal
USA	United States of America
VAS	visual analogue scale

STUDY SYNOPSIS

Protocol number: SHP626-201	Drug: Volixibat potassium (SHP626)
Title of the study: A Phase 2 Double-Blind, Randomized, Placebo-controlled, Dose-finding Study to Evaluate the Safety, Tolerability and Efficacy of Volixibat Potassium, an Apical Sodium-Dependent Bile Acid Transporter Inhibitor (ASBTi) in Adults with Nonalcoholic Steatohepatitis (NASH)	
Number of subjects (total and for each treatment arm): Approximately 677 subjects will be screened to enroll 266 subjects to achieve 201 completers. After enrollment of at least 80 subjects (20/treatment arm – 3 active and 1 placebo [PBO]) a 24-week interim analysis (IA) will eliminate at least one dose group based on the criteria provided to the Data Monitoring Committee; enrollment will continue to include approximately 67 subjects in each of the remaining arms. The sample size target for this study is 67 completers in each of the treatment groups (201 total if 3 arms continue). Including an additional 20 subjects to account for one dose dropped at the IA, 221 subjects are needed. Therefore, approximately 266 (accounts for 20% of 221 dropping out) subjects will be randomized if three arms (2 SHP626 and 1 PBO) continue; 208 (accounts for 20% of dropouts) subjects are needed if two SHP626 doses are dropped at the IA.	
Investigator(s): Multicenter study	
Site(s) and Region(s): Anticipated regions -US, Canada, and EU Estimated number of sites planned – 60 to 80	
Study period (planned): July 2016 to July 2020	Clinical phase: 2
Objectives: Primary: To evaluate the effect of volixibat compared to PBO on liver histology Secondary: 
• To evaluate the safety and tolerability of volixibat compared to PBO• To evaluate the effect of volixibat compared to PBO on hepatic steatosis (measured by MRI)• To evaluate the effect of volixibat compared to PBO on liver histology (measured by individual nonalcoholic fatty liver disease (NAFLD) activity score (NAS) components and fibrosis stage)• To evaluate the effect of volixibat compared to PBO on liver histology (measured by NASH resolution without worsening fibrosis)• To evaluate the effect of volixibat compared to PBO on serum liver-related biochemistry• To evaluate the effect of volixibat compared to PBO on metabolic indicators (glucose, insulin, hemoglobin A1c [HbA1c])• To evaluate the effect of volixibat compared to PBO on serum lipids (cholesterol, HDL-C, LDL-C, triglycerides)	
Rationale: Currently, there is no approved medication for the treatment of NASH. Volixibat is under development for the treatment of NASH based on its mechanism of action (MOA) and is supported by nonclinical and Phase 1 data. This is a Phase 2, 48-week, dose-finding study to examine the efficacy, tolerability, and safety of volixibat in adults with NASH.	
Investigational product, dose, and mode of administration: 
• Volixibat 5, 10, and 20 mg and matched PBO capsules by mouth (PO) once daily (QD). Investigational product (IP) should be given 30 minutes prior to the first meal of the day containing approximately 10-20	

grams of fat. Also see Section 6.2.3 (Dosing).

- Identical PBO will be used as comparator
 - Subjects should take the IP at the same time each day and should not take more than one dose in a day if they miss a dose. If a dose is missed at the normally scheduled time, the subject can make up the dose that day as long as no more than 1 dose is taken in a 10-hour period.

Methodology:

This study will be a Phase 2, 48-week, multicenter, double-blind, randomized, PBO-controlled, parallel group, proof of concept, dose-finding study, with one IA after at least 80 subjects have received 24 weeks of treatment. There will be 3 active arms of volixibat (5, 10 and 20 mg) and a PBO arm. Subjects will be randomized to receive one of three doses of volixibat (5, 10, or 20 mg once daily (QD) or PBO in a 1:1:1:1 ratio. Subjects with fibrosis stages F0 through F3 may be enrolled, but the number of F0 subjects will be capped at 81 if 1 dose is dropped after the interim analysis and at 62 if 2 doses are dropped. Depending on the results of the IA, the study may be terminated or the randomization to one or two doses will be stopped. The follow-up period will be 4 weeks after last dose. Subjects will be expected to visit the study center at least 10 times.

Inclusion and exclusion criteria:

Inclusion Criteria:

1. An understanding, ability, and willingness to fully comply with study procedures and restrictions.
2. Ability to voluntarily provide written, signed, and dated (personally or via a legally-authorized representative, as applicable) informed consent to participate in the study.
3. Age 18-80 years inclusive. This inclusion criterion will only be assessed at the first screening visit.
4. Male, or non-pregnant, non-lactating female, who is sexually active and who agrees to comply with the contraceptive requirements of the protocol, or females of non-childbearing potential. Males and females of child-bearing potential who are sexually active must agree to use acceptable contraception during the study and 30 days following the last dose of the IP.
5. Presence of $\geq 5\%$ steatosis on screening MRI from a centrally read radiologist performed either during the screening period or within 6 months prior to the first visit.
6. Histologic confirmation of NASH without cirrhosis (F0-F3) from a centrally read liver biopsy performed either during the screening period or within 6 months prior to the first visit with a NAS of ≥ 4 with a score of at least 1 in each component (steatosis, lobular inflammation, and hepatocyte ballooning).

Exclusion Criteria:

1. Presence of or history of cirrhosis or evidence of decompensated liver disease (ie, ascites, variceal bleeding, etc.) or hepatocellular carcinoma.
2. History or presence of other concomitant liver disease as assessed by the investigator or determined by laboratory findings including, but not limited to: active hepatitis B virus (HBV) infection (hepatitis B surface antigen (HBsAg) positive and/or HBVDNA positive; subjects who are hepatitis B core antibody (HBcAb) positive may be eligible as long as HBsAg is negative and HBVDNA is nondetectable), active hepatitis C virus (HCV) infection (prior exposure to HCV [defined as HCVAb positive] without a current or prior history of a detectable HCV RNA) will be eligible, alcoholic liver disease, proven autoimmune hepatitis, primary biliary cirrhosis (PBC), primary sclerosing cholangitis (PSC), hemochromatosis, Wilson's disease, alpha-1 antitrypsin deficiency, bile duct obstruction, liver primary or metastatic cancer.
3. Current or recurrent disease that could affect the action, absorption, disposition, or laboratory assessment of the IP (including bile salt metabolism in the intestine) eg, uncontrolled inflammatory bowel disease, uncontrolled celiac disease, gastric bypass procedures (gastric lap band or gastric sleeve is acceptable), ileal or ileocecal resection, uncontrolled irritable bowel syndrome with predominant

diarrhea, or history of chronic diarrhea or loose stools of any etiology.

4. Weight change $\geq 5\%$ after qualifying liver biopsy and/or MRI performed. If the subject had a liver biopsy and/or MRI within 6 months of screening, but experienced a weight change $\geq 5\%$ since the date of liver biopsy and/or MRI, the liver biopsy and/or MRI must be repeated at screening.
5. Contraindications to MRI (ie, claustrophobia, coronary stents, coronary implantable devices, girth, etc.). Stents or other devices may be allowed, at the investigator's discretion, if they do not interfere with the functioning of the MRI machine.
6. Current or relevant history of physical or psychiatric illness, any medical disorder that may require treatment or make the subject unlikely to complete the study.
7. Treatment with Vitamin E, thiazolidinediones (TZD), or glucagon-like peptide-1 receptor agonists (GLP-1 RA) unless subject on a stable dose for 6 months prior to qualifying liver biopsy and not initiated after qualifying liver biopsy and will continue the same dosing regimen throughout study participation.
8. Uncontrolled diabetes defined as HbA1c of $\geq 9.5\%$ within 60 days prior to enrollment.
9. Current use of any medication (including over-the-counter, herbal, or homeopathic preparations) that could affect the action, absorption, or disposition of the IP, or clinical or laboratory assessment. (Current use is defined as use within 14 days of screening). Patients currently taking insulin will not be excluded; however, they must be on a stable dose for at least 30 days prior to screening, or a sliding scale of insulin is allowed as long as the subject's HbA1c remains $< 9.5\%$.
10. Use of drugs, herbs or supplements historically associated with causing or worsening NAFLD/NASH for less than 6 months prior to qualifying liver biopsy, or initiated any time after qualifying liver biopsy performed, including the use of total parenteral nutrition (TPN).
11. Serum AST > 7 times upper limit of normal (ULN) at screening.
12. Serum ALT > 7 times ULN at screening.
13. Elevated serum creatinine ≥ 2.0 mg/dL.
14. International normalized ratio (INR) > 1.3 .
15. Total bilirubin (TB) $\geq 2.0 \times$ ULN at screening (Except for documented Gilbert's syndrome with bilirubin levels 20 $\mu\text{mol/L}$ to 90 $\mu\text{mol/L}$ (1.2 to 5.3 mg/dL) and with a ratio of unconjugated/conjugated bilirubin that is commensurately higher).
16. Platelet count $< 130 \times 10^9/\text{L}$
17. Medical history of impaired hemostasis or current use of anticoagulant medication (use of antiplatelet medications, such as low-dose, ie, 81mg, aspirin (ASA) or clopidogrel (Plavix), will be allowed).
18. Uncontrolled thyroid disease.
19. Type 1 diabetes mellitus.
20. Known or suspected intolerance or hypersensitivity to the IP, closely-related compounds, or any of the stated ingredients.
21. Known history of alcohol or other substance abuse within the last year or at any time during the study based on investigator's discretion. Weekly alcohol intake greater than 21 grams/day for males and 14 grams/day for females on average or inability to reliably quantify alcohol consumption based on investigator's judgment.
22. Within 6 months of MRI and liver biopsy:
 - Have used any IP
 - Have been enrolled in a clinical study (including vaccine studies) that, in the investigator's


opinion, may impact this Shire-sponsored study
 
23. Inability to safely obtain a liver biopsy.
 
24. Females who are pregnant, planning to become pregnant, or are breastfeeding, or males who are planning to father a child during study participation.
 
25. The anticipated need for a surgical procedure during the study that could interfere with the treatment.
 
26. Known positivity for human immunodeficiency virus (HIV) infection.
 
27. Cancer within 5 years of screening, except for basal or squamous cell carcinoma of the skin or in situ cervical carcinoma that has been treated with no evidence of recurrence.
 
28. History of noncompliance with medical regimens, unreliability, mental instability or incompetence that could compromise the validity of informed consent or lead to noncompliance with the study protocol.
 
29. Any other conditions or abnormalities which, in the opinion of the investigator, may compromise the safety of the subject, or interfere with the subject participating.
 
30. Subject is currently enrolled in this study at any study site (unless the subject is transferring to another qualified study site with prior sponsor approval).
 
31. Subjects who are employees at the unit of the investigational site that is conducting the study.

Maximum duration of subject involvement in the study:
 
• Planned duration of screening period: 56 days• Planned duration of enrollment period: 364 days• Planned duration of treatment period: 336 days• Planned duration of follow-up: 28 days

Endpoints and statistical analysis:
 
Safety Analysis Set will consist of all subjects who take at least 1 dose of randomized IP, and have at least 1 post-baseline safety assessment (eg, coming back for any visit, reporting of an adverse event (AE) or reporting the absence of AEs).
 
Full Analysis Set (FAS) will consist of all subjects in the Safety Analysis Set who have at least 1 post-baseline efficacy assessment (eg, MRI, liver biopsy, serum liver-related biochemistry measurement).
 
Interim Analysis Set (IAS) will consist of all subjects in the Safety Analysis Set who have at least 1 post-baseline efficacy assessment (eg, MRI, ALT biochemistry measurement) on or before the Week 24 visit at the time of the data cut for the IA.
 
Screened Set will consist of all subjects who have signed an informed consent.
 
Randomized Set will consist of all subjects in the Screened Set who have been randomized into the study.

Efficacy Endpoints:
 
• Primary: Binary response indicating (yes/no) whether a subject responded at Week 48 with a reduction of at least 2 points without worsening of fibrosis from baseline NAS.• Secondary:
• Change from baseline to Week 48 on liver histology as measured by the individual NAS components (ballooning, inflammation, steatosis).• Change from baseline to Week 48 on hepatic steatosis as measured by MRI-PDFF.• Change from baseline to Week 48 on liver histology as measured by fibrosis stage. (NASH Clinical Research Network (CRN))

- Resolution of NASH (defined as total absence of ballooning [score = 0] absent or mild inflammation [score 0-1], steatosis can be present [score 0-3]), without worsening of fibrosis as assessed by liver histology at week 48.
- Change from baseline to Week 48 on serum liver-related biochemistry as measured by:
 - alanine aminotransferase (ALT)
 - aspartate aminotransferase (AST)
 - alkaline phosphatase (ALP)
 - gamma glutamyl transferase (GGT)
 - total bilirubin (TB)
- Change from baseline to Week 48 on metabolic indicators as measured by:
 - fasting serum glucose levels
 - insulin levels
 - HbA1c
- Change from baseline to Week 48 on serum lipids measured by:
 - fasting total cholesterol
 - HDL-C
 - LDL-C
 - triglycerides

Primary hypotheses:

